Secondary Objectives	
• To measure overall radiographic response (by RECIST v1.1 and mRECIST) 6 months after the date of the first planned DEB-TACE procedure.• To measure time to untreatable progression (TTUP). TTUP is defined as time to disease progression untreatable by liver-directed percutaneous or surgical methods.• To measure median time to progression (TTP)• To measure hepatic progression free survival (HPFS)• To measure progression free survival (PFS)• To measure overall survival (OS)• To determine the proportion of patients who remain active on the wait list for a liver transplant and eventually are transplanted.• To determine the proportion of patients who are inactivated or drop out from the wait list for any reason but transplantation.• To determine the proportions of patients who are successfully down-staged and achieve active waitlist status and eventually are transplanted.• To measure proportion with alpha-fetoprotein (AFP) response with $\geq 50\%$ decline from baseline (in patients with baseline level ≥ 20) post DEB-TACE and test for association with hepatic and overall response rate, PFS, and OS• To determine whether cardiac function changes occur as a result of DEB-TACE with doxorubicin• To obtain pharmacokinetic data for doxorubicin administered as a part of DEB-TACE procedures

Abstract

Study Design	Prospective open-label two-stage phase II clinical trial to evaluate the safety and efficacy of DEB-TACE in patients with liver-only HCC and significant hepatic dysfunction who are being considered for a liver transplant.
Number of patients	17 patients will be enrolled into the first stage of the study for safety and efficacy 34 patients will be enrolled into the second stage of the study
Duration of Therapy	Most patients will need only one DEB-TACE treatment, performed within 60 days of Screening procedures For patients that have more than one treatment, the procedure will be done about 4 weeks after the first, or previous treatment, up to 4 treatments total
Duration of Follow up	Post Treatment Evaluation will last 1 year
Duration of study	The study will reach completion 5 years from the time the study opens to accrual

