At UCSF and other transplant centers, patients with HCC confined to the liver may be offered a spot on the liver transplant list. Expected 5-year survival in patients with HCC who make it to liver transplant is 70-90%, which is better than that for surgery (50%) or liver-directed therapy alone (20-50%) (1). A chief requirement for listing is tumor burden within United Network for Organ Sharing (UNOS) T2 stage (one lesion less than 5 cm or up to 3 lesions each less than 3 cm in size). Patients with UNOS T3 stage (disease confined to the liver without evidence imaging evidence of portal or hepatic vein invasion or extracapsular extension) may also be listed if they undergo successful “down-staging” to UNOS T2 or T1 using liver-directed therapy (7, 8). Liver-directed therapy choices include transarterial chemoembolization (TACE), SIRT, radiofrequency ablation (RFA), and percutaneous ethanol injection (PEI). Typical wait for an organ in UNOS region 5, which includes California, is 1.5-2 years depending on the patient’s blood type. If untreated, HCC is likely to progress during this long waiting period beyond UNOS T2 stage. Therefore, various liver-directed treatment approaches including TACE, RFA, and PEI are

employed to maintain patients active on the transplant list.

TACE is a standard treatment option for patients with intermediate stage, unresectable hepatocellular carcinoma (HCC) without significant hepatic synthetic dysfunction (2). TACE produces an objective tumor response rate of 35%-40% and confers a significant survival advantage as compared to best supportive care (9, 3, 4). Improved quality of life and reduced pain following initiation of chemoembolization are reported among patients undergoing sequential TACE (10). Current indications for TACE include first line treatment for unresectable intermediate stage HCC, as “bridging” therapy to prevent disease progression and drop-out on the liver transplant waiting list, as a method to “down-stage” patients to qualify them for liver transplantation, or enable liver resection through the reduction of disease burden (2, 7).

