4.2 Inclusion Criteria

1. Adult male or female patients, age 18 years of age or older
2. Diagnosis of liver-only HCC based on European Association for the Study of the Liver (EASL) criteria (radiographic lesion appearance on contrast-enhanced CT or MRI, i.e. enhancement on early arterial phase, washout on portal venous phase with or without associated elevation of serum AFP level $>200\text{U/ml}$) or histologic confirmation of HCC diagnosis, whichever is applicable.
3. UNOS stage T1, T2, or T3 disease.
4. Candidates for liver transplantation (listed or screened) according to one of the following criteria:
 - a. Milan criteria (one lesion $< 5\text{cm}$ or 3 or fewer lesions each $< 3\text{cm}$),
 - b. UCSF Downstaging criteria (one lesion less than 8 cm or 2-3 lesions each less than 5 cm with sum of maximum dimensions less than 8 cm, or 4-5 lesions each less than 3 cm with sum of maximum dimensions less than 8 cm)
 - c. UCSF All-Comers criteria (UNOS stage T3 disease beyond UCSF Downstaging Criteria).
5. At least one measurable site of disease in the liver according to RECIST version 1.1 and mRECIST criteria.
6. **At least one** of the following clinical, laboratory, or imaging parameters:
 - a. Mild or moderate ascites
 - b. Serum bilirubin $\geq 3\text{ mg/dl}$ but less than 6 mg/dl
 - c. Aspartate aminotransferase (AST) > 5 times upper limit of normal (ULN) but ≤ 10 times ULN
 - d. Alanine aminotransferase (ALT) > 5 times upper limit of normal (ULN) but ≤ 10 times ULN
 - e. International normalized ratio for prothrombin time (INR) >1.5 but ≤ 2.5
 - f. Bland portal vein thrombosis (branch or main)
 - g. Functioning transjugular intrahepatic portosystemic shunt (TIPS) or surgical portosystemic shunt
7. ECOG performance status of 0, 1, or 2.
8. Ability to give written informed consent.

Patients should meet the above study entry criteria at study enrollment as well as prior to undergoing each subsequent DEB-TACE procedure.

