12.3 Analysis Plan

Demographics and Baseline Characteristics

Demographic and baseline laboratory results will be summarized using descriptive statistics.

Safety Analysis

Patients will be monitored for development of recognized complications of DEB-TACE including liver dysfunction, renal dysfunction, ascites, hepatic encephalopathy, hepatorenal syndrome, biliary injury (stricture or leak), cholangitis, cholecystitis, hepatic abscess, abdominal pain, nausea, vomiting, fatigue, and fever. Adverse events will be graded according to NCI CTCAE version 4.03. Prevalence of adverse events will be summarized using descriptive statistics.

Efficacy Analyses

Analyses will be performed using the intent to treat population with exceptions as defined below, which require patient replacement.

Primary efficacy analysis

Primary efficacy will be evaluated as 1-month radiographic response after last DEB-TACE procedure in treated HCC lesions according to 1) RECIST version 1.1 and 2) mRECIST. Patients who do not have any post-baseline tumor assessments will be counted as non-responders. Point estimates of response rate and confidence intervals will be provided.

Secondary efficacy analyses

1. Overall radiographic response by 1) RECIST 1.1 and 2) mRECIST 6 months after the date of the first planned DEB-TACE procedure. This analysis will take into account all measurable hepatic HCC lesions present on cross-sectional imaging 6 months after the date of the first planned DEB-TACE procedure.
2. Time to untreatable progression (TTUP). TTUP is defined as time to disease progression untreatable by liver-directed percutaneous or surgical methods as assessed by treating investigator(s). Patient follow-up up to 1 year after last DEB-TACE will be allowed for this outcome variable.
3. Time to progression (TTP). TTP is defined as the time interval between date of first DEB-TACE procedure and date of imaging documenting development of intra- or extrahepatic disease progression by 1) RECIST 1.1 and 2) mRECIST. Patient follow-up up to 1 year after last DEB-TACE will be allowed for this outcome variable.

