4. Hepatic progression-free survival (HPFS). Hepatic progression-free survival rate will be defined as the number of patients who neither progressed in the treated regions of the liver (using RECIST 1.1 and mRECIST) nor died before 1, 3, 6, 9, and 12 months after date of last DEB-TACE over the number of patients who entered the trial at these same timepoints. Estimates of the HPFS curves from the Kaplan-Meier method will be presented. Median progression event time and a 2-sided 95% confidence interval for the median will be provided using a normal approximation. For each stratum, the median, 25th and 75th percentile for HPFS will be provided.
5. Progression-free survival (PFS). Progression-free survival rate will be defined as the number of patients who neither progressed (using RECIST 1.1 and mRECIST) nor died before 1, 3, 6, 9, and 12 months after date of last DEB-TACE over the number of patients who entered the trial at these same timepoints. Estimates of the PFS curves from the Kaplan-Meier method will be presented. Median progression event time and a 2-sided 95% confidence interval for the median will be provided using a normal approximation. For each stratum, the median, 25th and 75th percentile for PFS will be provided.
6. Overall Survival (OS) is a secondary efficacy endpoint and will be analyzed 12 months after the last patient is enrolled. OS will be calculated from date of first DEB-TACE until date of death, using chart review and/or follow up phone calls to determine date of death in patients after removal from study. The survival of patients who are permanently lost to follow-up or still alive after 360 days of follow up post study discontinuation will be censored on the date the patient is last-contacted or last known to be alive. Estimates of the OS curves from the Kaplan-Meier method will be presented.
7. Proportion of patients who remain active on the waitlist and are eventually transplanted is a secondary clinical endpoint. This data will be presented using Kaplan-Meier method
8. Proportion of patients who are inactivated or drop out from the wait list for any reason but transplantation will be determined. Reasons for inactivation and/or removal from waitlist will be tabulated.
9. Proportions of patients who are successfully down-staged and achieve active waitlist status and eventually are transplanted will be determined.

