10. Biochemical response defined as $\geq 50\%$ decrease in alpha-fetoprotein level measured 1 month and 4 months after DEB-TACE.
11. Histopathologic response defined as percentage of tumor necrosis at liver explant histopathology. This will only be explored in the subgroup of patients who undergo a liver transplant. Per UCSF clinical standard, tumor necrosis for HCC lesions is reported as 100%, >90%, 60-90%, 30-59%, and < 30%.

Intention To Treat Exceptions (Patient replacement)

1. Patients who proceed to liver transplant or develop hepatic decompensation between the time of enrollment and the first DEB-TACE treatment will be replaced.
2. Patients who proceed to liver transplant prior to completion of the 1 month safety window after first DEB-TACE will be replaced unless the transplant occurred due to hepatic decompensation or other toxicity attributed as at least possibly-related to protocol therapy, in which case the hepatic decompensation or other toxicity will be deemed a serious adverse event and the patient will be included in safety analysis (see Section 14.1.3).

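### Kaplan-Meier does not estimate the transplant proportion in item 7, the PFS and HPFS rates can disagree with their own curves, and TTUP follow-up needs reconciling with the removal rules

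*Combined protocol and SAP*

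**What the plan says.** All references are to the combined protocol and SAP.

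- **Wait-list outcomes (12.3, items 7-9).** Item 7 concerns "patients who remain active on the waitlist and are eventually transplanted is a secondary clinical endpoint. This data will be presented using Kaplan-Meier method". It defines no event, origin or censoring. Item 8 is separate: "Proportion of patients who are inactivated or drop out from the wait list for any reason but transplantation will be determined". Item 9 covers patients first down-staged to active status. Section 4.2 admits "Candidates for liver transplantation (listed or screened) according to one of the following criteria".
- **PFS and HPFS (12.3, items 4 and 5).** Each rate is the number neither progressed nor dead at 1, 3, 6, 9 and 12 months; the wording of the ratio ends "months after date of last DEB-TACE over the number of patients who entered the trial at these same timepoints". Each item also plans a Kaplan-Meier curve. Section 12.3 sets the intent-to-treat population with listed exceptions, one of which is "Patients who proceed to liver transplant prior to completion of the 1 month safety window after first DEB-TACE will be replaced" (transplants that followed treatment-related toxicity are not replaced). The only censoring rule in 12.3 is the one for OS.
- **TTUP (12.3, item 2).** "Patient follow-up up to 1 year after last DEB-TACE will be allowed for this outcome variable".
- **Removal (8.4.1, 8.4.2, 10.3).** Assessments stop, or the patient leaves the study, on transplant or when another anti-cancer modality such as ablation, surgery or conventional TACE is required. After removal, item 6 provides chart review or phone calls for date of death only.

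**The concern.** A patient who dies or leaves the list cannot be transplanted, and a transplanted patient cannot drop out. Kaplan-Meier treats a censored patient as still able to have the event later. Censoring one of these outcomes therefore estimates the other in a world where the first does not happen, which is not the proportion that item 7 names.

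For PFS and HPFS, leaving the study progression-free through transplant is an expected and desired outcome in this population. Such a patient has neither progressed nor died, stays in an intent-to-treat denominator, and is no longer assessed. The crude ratio carries that patient as progression-free to month 12. The Kaplan-Meier curve in the same item would presumably stop counting at removal. One report could then give two different 12-month values.

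For TTUP, a patient whose progression can still be ablated or resected leaves assessment before untreatable progression can be seen, unless item 2 is meant to reach past removal.

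At stake is the description of bridging to transplant, which is the trial's stated rationale.

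**Working it through.** The plan gives no figure for these items, so there is none to reproduce. Its design figures do reproduce by exact binomial sums: early stopping 0.758 at 20% and 0.126 at 40%, power 0.854, type I error 0.0487. None bears on this point.

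**Item 7**

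*Inputs.* Section 1.1: "Typical wait for an organ in UNOS region 5, which includes California, is 1.5-2 years". I take this as a median running from DEB-TACE, which is an assumption. Yearly drop-out or death, d, is not in the documents; I assume 10%, 20% and 30%. Hazards are constant.

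*Formulas (T in months).* λT = ln 2/18 or ln 2/24; λD = −ln(1−d)/12; L = λT + λD.

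- Transplant, 1−KM = 1 − exp(−λT·T)
- Transplant, cumulative incidence = (λT/L)·(1 − exp(−L·T))

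*Example.* Median 18, d = 0.30, T = 24: λT = 0.0385, λD = 0.0297, L = 0.0682. 1−KM = 0.603; cumulative incidence = 0.564 × (1 − 0.194) = 0.455; gap 14.9 points.

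| Median wait | d | 12 months: 1−KM / CIF / gap (%) | 24 months: 1−KM / CIF / gap (%) |
|---|---|---|---|
| 18 mo | 10% | 37.0 / 35.3 / 1.7 | 60.3 / 55.3 / 5.1 |
| 18 mo | 20% | 37.0 / 33.5 / 3.6 | 60.3 / 50.3 / 10.0 |
| 18 mo | 30% | 37.0 / 31.6 / 5.5 | 60.3 / 45.5 / 14.9 |
| 24 mo | 10% | 29.3 / 27.9 / 1.4 | 50.0 / 45.6 / 4.4 |
| 24 mo | 20% | 29.3 / 26.4 / 2.9 | 50.0 / 41.4 / 8.6 |
| 24 mo | 30% | 29.3 / 24.9 / 4.4 | 50.0 / 37.2 / 12.8 |

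Gaps are taken before rounding.

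*Drop-out as the event, transplant censored.* Exchange λT and λD in the formulas. In the example, 1−KM is 51.0% against a cumulative incidence of 35.1%, a gap of 15.9 points. Over the grid, drop-out is overstated by 1.5-5.6 points at 12 months and 5.1-15.9 at 24.

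*Sensitivity.* With the transplant rate halved, because some patients are only screened or must first be down-staged, the transplant gaps are 0.8-3.2 points at 12 months and 2.7-9.8 at 24.

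*Scale.* The 95% half-width for 30% of 51 is 1.96 × √(0.3 × 0.7/51) = 12.6 points.

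**Items 4 and 5**

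*Inputs.* Single-session patients (Abstract, Duration of Therapy: "Most patients will need only one DEB-TACE treatment"); no transplants in month 1, given the replacement rule; an assumed 12-month PFS of 50% on the Kaplan-Meier scale that censors at removal; λT as above.

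*Formulas.* a = ln 2/12 = 0.0578.

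- Still assessed and event-free at 12 months = exp(−12a)·exp(−11λT) = 0.327 (18 mo), 0.364 (24 mo)
- Transplanted progression-free by then = exp(−a)·[λT/(λT + a)]·(1 − exp(−11(λT + a))) = 0.247, 0.193, or 12.6 and 9.9 of 51 patients
- Crude ratio = sum = 0.574, 0.557

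So the ratio is 56-57% where the curve gives 50%. At half the transplant rate it is 53-54%. If the curve gives 30%, the full-rate ratio is 37-39%. Removal for other therapy is not modelled here and would push the same way.

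**TTUP**

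No arithmetic applies. Item 2 permits follow-up to one year after the last procedure. Sections 8.4.1 and 8.4.2 stop assessments earlier when another modality is needed, and 10.3 removes the patient. Untreatable progression is itself a removal reason, so it is recorded when it comes first. No passage says whether it is sought after removal for another reason.

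**The case against.** **Item 7 does not say that transplant is the event.** This stands. A reader might infer that the bias must favour the treatment, but the documents do not support that. The direction depends on which outcome is the event; what is fixed is that neither curve estimates the stated proportion. Item 9 also suggests that item 7 means patients already active on the list, and item 8 reports drop-out separately. Both narrow the gap, but the denominator is still not stated and the two outcomes are not combined.

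**The PFS ratio is less open than it looks.** A reader might infer that the 12-month rate could fall anywhere from 33% to 57%, according to whether progression-free removals count as failures (33-36%), are left out (43-45%) or count as progression-free (56-57%). The first conflicts with the numerator wording, since these patients neither progressed nor died. The second sits badly with the intent-to-treat population. Only the third fits the text, and its excess is 3-7 points against a half-width of 13.7 points for 50% of 51.

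**Constant hazards flatter the PFS effect.** Largely right. With a rising transplant hazard (Weibull shape 2 or 3, same medians), the ratio falls to 51-54%. The item 7 gap at 24 months does not shrink.

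**Censoring at transplant is an estimand choice.** Fair, and it is why 50% is called here the Kaplan-Meier value, not the truth. The need is for one stated rule that the rate and the curve share.

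**TTUP follow-up may be meant to continue after removal.** Possible. A reader might infer that untreatable progression after other therapy is not collected. The documents do not say so; they leave it unresolved.

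**Conclusion.** The point holds for secondary endpoints only.

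- **Item 7:** the named method does not estimate the named proportion under the usual censoring. The overstatement of transplant, if that is the event, is about 1-6 points at 12 months, which is modest beside the sampling error. It is 4-15 points at 24 months, where the upper end exceeds the 12.6-point half-width. If drop-out is the event, it is overstated by similar amounts. The sizes rest on constant hazards, a 1.5-2 year median wait and 10-30% yearly drop-out or death; the last range is wholly assumed.
- **PFS and HPFS:** the crude rate exceeds the Kaplan-Meier value that censors at removal, about 53-57% against 50% in the illustration, and by less if the transplant hazard rises over time. The inconsistency between rate and curve matters more than its size.
- **TTUP:** the passages must be reconciled; the effect cannot be sized from the documents.

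The primary response decision and N=51 are untouched. The changes are worth making because they are cheap and best settled before data are seen.

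**What to change.** 1. **Item 7:** name the event, the time origin and the denominator (for example, listed at entry or ever listed). Report the cumulative incidence of transplant with death and drop-out or inactivation as competing events, alongside item 8.
2. **Items 4 and 5:** read the 1-12 month rates from the Kaplan-Meier curves already planned, with a stated censoring rule for transplant and other removal, in place of the crude ratio.
3. **TTUP:** reconcile item 2 with 8.4.1, 8.4.2 and 10.3 for data collection only. One way is to add untreatable progression, wait-list status and transplant date to the chart review planned for OS, up to item 6's horizon of 360 days after discontinuation. Early leavers and late entrants will have less than 24 months of follow-up, so show numbers at risk.

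The cost is SAP wording and three fields in a review already planned, with no new visits or scans. There are downsides. Censoring at removal assumes that removal is unrelated to progression risk. Untreatable progression read from charts is less standardised than study imaging, and a phone call alone is a weak source for it. The figures may look less favourable. No change to treatment or removal rules is proposed.

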2.0 OBJECTIVES

Primary Objective

- To determine the safety of DEB-TACE in patients with HCC confined to liver who are being considered for liver transplantation
- To determine the response rate to DEB-TACE by conventional and modified Response Evaluation Criteria in Solid Tumors (RECIST version 1.1, mRECIST [22]) for treated lesions in patients with liver-only HCC who are being considered for liver transplantation.

Secondary Objectives

- To measure overall radiographic response (by RECIST v1.1 and mRECIST) 6 months after the date of the first planned DEB-TACE procedure. To measure time to untreatable progression (TTUP). TTUP is defined as time to disease progression untreatable by liver-directed percutaneous or surgical methods.
- To measure median time to progression (TTP)
- To measure hepatic progression free survival (HPFS)
- To measure progression free survival (PFS)
- To measure overall survival (OS).
- To determine the proportion of patients who remain active on the wait list for a liver transplant and eventually are transplanted.
- To determine the proportion of patients who are inactivated or drop out from the wait list for any reason but transplantation.
- To determine the proportions of patients who are successfully down-staged and achieve active waitlist status and eventually are transplanted.
- To measure proportion with alpha-fetoprotein (AFP) response with $\geq 50\%$ decline from baseline (in patients with baseline level ≥ 20) post DEB-TACE and test for association with hepatic and overall response rate, PFS, and OS.
- To determine whether changes in cardiac function occur as a result of DEB-TACE with doxorubicin
- ***To obtain pharmacokinetic data for doxorubicin administered as a part of DEB-TACE procedures***

Exploratory/Other Objectives

- To describe treatment response by histopathology at the time of liver transplantation (in the subgroup of patients who undergo LT).

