12.0 STATISTICAL CONSIDERATIONS

12.1 Basis for Sample Size

This is an open label single arm phase II study. The primary objective is to assess the safety and to estimate the objective response rate using mRECIST in treated lesions to the DEB-TACE treatment. The response rate is assumed to be >40% in treated lesions using mRECIST on imaging approximately 1 month after last planned DEB-TACE treatment; the response rate of <20% would be unacceptable for the study treatment. If the response rate is less than a pre-specified minimum goal (i.e. 20%) then the study will be terminated due to inefficacy. Under binomial approximation with 5% type I error and 85% power, a total of 51 patients is required for the study; 17 patients will be accrued in the first stage and 34 patients will be accrued in the second stage.

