12.2 Interim Analysis

After 17 patients have received at least one DEB-TACE and had potential for at least 4 weeks of follow up, the safety profile will be analyzed. The study will be terminated if one of the termination criteria based on unacceptable toxicity listed in section 10.0 has occurred. Final review of the safety will be performed within approximately three months after the treatment of the 17th patient. Stopping rules for lack of safety and efficacy after first stage are defined in Section 10.0. Accrual will continue during these interim analyses.

During the interim efficacy analysis of 17 patients, if four or fewer responses by mRECIST in treated lesions on imaging approximately 1 month after last planned DEB-TACE are observed during the first stage, the study will be stopped early; otherwise, additional 34 patients will be

accrued. If fourteen or fewer responses by mRECIST in treated lesions on imaging approximately 1 month after last planned DEB-TACE are observed by the end of the study, then no further investigation is warranted for the regimen.

Under the study design, if the response rate is <20%, the probability of ending the study during the first stage is 76%. If the response rate is >40%, the probability that the study will be stopped in the first stage is 13%.

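### AFP change is reduced to a 50% yes/no cut before it is tested against response, PFS and OS, which discards information in a subset of at most 51 patients

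*Combined protocol and SAP*

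**What the plan says.** The Abstract and section 2.0 Objectives list, as a secondary objective, the proportion of patients with an AFP decline of at least 50%. It is restricted by the words "in patients with baseline level" of at least 20. The same sentence continues "post DEB-TACE and test for association with hepatic and overall response rate, PFS, and OS". The variable to be tested is therefore the 50% indicator, within the restricted subset.

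Section 12.3, secondary efficacy item 10, is the only analysis text. It defines biochemical response as a 50% or greater "decrease in alpha-fetoprotein level measured 1 month and 4 months after DEB-TACE". It does not repeat the baseline restriction, names no association test and plans no analysis of AFP as a continuous quantity.

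The numeric values are collected anyway. AFP is taken before treatment and, under sections 8.4.1 and 8.4.2, from about 30 days after the last planned procedure.

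**The concern.** With a cut at 50%, a 49% fall is handled like a rise, and a 51% fall like a 99% fall. When the underlying relation is smooth, that discards information the trial already holds. The patients available are those of the 51 with baseline AFP of at least 20, and the documents do not say how many that is. At stake is the sensitivity of a stated secondary objective that commits to a test. No stopping rule and no primary conclusion depends on it.

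**Working it through.** **1. The plan's own figure.** Section 12.1 states: "Under binomial approximation with 5% type I error and 85% power, a total of 51 patients is required for the study". Inputs from sections 12.1 and 12.2: n1=17, stop at 4 or fewer; n=51, negative at 14 or fewer; p0=0.20, p1=0.40. Early stopping probability is P(X1≤4) with X1~Bin(17,p). The probability of success is the sum over x=5 to 17 of P(X1=x)·P(X2≥15−x), with X2~Bin(34,p). Results: type I error 4.87%, power 85.4%, early stopping 75.8% at p=0.20 and 12.6% at p=0.40. The stated 5%, 85%, 76% and 13% reproduce. They concern the primary endpoint in all 51 patients; no power is stated for the AFP tests.

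**2. Information kept by the cut.** For a normal covariate split so that a share q falls on one side, relative efficiency is RE = φ(z_q)² / [q(1−q)].

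| AFP responder share q | RE | 30 patients on the cut equal |
|---|---|---|
| 50% | 0.398942²/0.25 = 0.64 | 30×0.64 ≈ 19 |
| 30% (or 70%) | 0.3477²/0.21 = 0.58 | 30×0.58 ≈ 17 |
| 20% (or 80%) | 0.2800²/0.16 = 0.49 | 30×0.49 ≈ 15 |

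**3. Power against tumour response (simulation, two-sided 5%).** All inputs here are assumptions: 20 to 40 eligible patients; 40% tumour responders; a normal log AFP ratio differing by 0.8 to 1.2 SD between responders and non-responders; 30% or 50% of patients past the cut. The 40% echoes section 12.1 ("The response rate is assumed to be >40% in treated lesions using mRECIST on imaging"), which is the planning value for 1-month treated-lesion response, not for every response measure in the objective.

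| Setting | Cut, chi-square | Continuous, rank test |
|---|---|---|
| n=20, 0.8 SD | 25–27% | 33–34% |
| n=30, 1.0 SD | about 53% (Fisher about 43%) | about 67% |
| n=40, 1.0 SD | 64–65% | 81% |
| n=20, 0.5 SD | 12% | 14% |
| n=30, 0.5 SD | 15% | 21% |

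Across 0.8 to 1.2 SD the gap is about 4 to 17 points against chi-square. It is wider against Fisher, partly because that test is conservative.

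**4. Power for time to event.** Power = Φ(√(n·e·RE)·|ln HR| − 1.96), where e is the share with events, HR is per SD, and RE=1 for the continuous value. Worked case with n=30, e=0.6, HR 2: continuous √18×0.693−1.96 = 0.98, giving 84%; cut at q=0.5, √(18×0.637)×0.693−1.96 = 0.39, giving 65%.

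| Setting | Cut | Continuous |
|---|---|---|
| n=20, 70% events, HR 2 | 50–54% | 74% |
| n=30, 70% events, HR 2 | 67–72% | 89% |
| n=51, 70% events, HR 1.5 | 45–49% | 68% |
| n=30, 20% events, HR 2 | 27% | 40% |
| n=20–30, 15–25% events, HR 1.6 | 10–18% | 13–25% |

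The last two rows are closer to what OS might look like if few patients die. The documents give no event rate.

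**5. When AFP is known.** Section 12.3 counts OS from the first procedure and the PFS rates from the last. AFP follows the last procedure by about 30 days. With four procedures a month apart (section 8.3), that is about 3×30+30 = 120 days after OS begins. A patient must survive that interval to have the value at all.

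**The case against.** Several points on the other side stand.

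- **The tests are secondary and unpowered.** In a single-arm phase II trial with no decision attached to these tests, a prespecified responder definition is a defensible choice, and the lack of a cited guideline for 50% is not an error.
- **Small numbers are the larger problem.** Where the cut usually fails (n=20, 0.8 SD), the continuous test usually fails too.
- **The shape is assumed.** If the true relation is a step at the cut, the ranking reverses: at n=30, with response in 60% against 20%, power is 62% for the cut and 48% for the rank test. The documents cannot settle this.
- **The responder share is uncertain.** Section 10.2 counts stable disease as response, and overall response is read at 6 months, so 40% may not apply.
- **Follow-up is truncated.** Assessments stop at transplant or another anti-cancer treatment, which limits PFS events.

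A reader might infer that the cut is likely to turn a real association into a null result. The figures do not support that as a general statement: at n=40 and 1.0 SD the cut detects the association about 64% of the time, and at 1.2 SD about 80%.

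It might also be said that item 10 names no test, so nothing is dichotomised. That does not stand, because the objective's only AFP variable is the 50% indicator, and it is the quantity to be tested.

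**Conclusion.** The point holds as an avoidable loss of sensitivity in a secondary analysis. With a roughly normal log AFP change and a smooth relation to outcome, the cut gives up 36% to 51% of the information. Under the assumed inputs this costs about 4 to 17 points of power against response. For PFS the cost could be around 20 points if events are common and the effect is large; for OS with few deaths, neither analysis is informative. The eligible share, the AFP distribution, the AFP responder rate and the event rate are all assumptions, because the documents give none of them. A simple swap to Cox regression on the AFP value would not be enough: time before the AFP measurement must be handled.

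**What to change.** In section 12.3 item 10:

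- Restate the restriction to baseline AFP of at least 20.
- Keep the proportion with a decline of at least 50% as the descriptive summary, and show its association with outcome as a supportive display.
- Run the main association tests on the continuous log ratio of 1-month to baseline AFP: logistic regression or a rank test for response, and Cox regression for PFS and OS.
- For PFS and OS, count time from a landmark at the AFP measurement, or enter AFP as a time-dependent covariate.
- State the role of the 4-month value. The AFP visits are at 30, 90, 180, 270 and 360 days, so none falls at 4 months.
- Label the tests as exploratory, with low power.

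The cost is wording only, with no new visits or samples. An effect per halving of AFP is slightly less familiar to clinicians than a responder contrast, which is still shown. With a landmark, patients who have an event or are censored before it drop out of the PFS and OS tests, and their number should be reported.
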